9.5 Pharmacokinetic/Pharmacodynamic Analyses

PK/PD analyses or graphical explorations may be used to assess the relationship between LY3493269 doses and/or concentrations and

- Safety parameters, such as
 - QT interval corrected using Fridericia's formula (QTcF) interval
 - Blood pressure
 - Heart rate (HR)
 - PR interval,
- Tolerability parameters, such as
 - nausea

- vomiting
- diarrhea,
- PD parameters, such as
 - fasting glucose
 - fasting insulin
 - fasting C-peptide
 - fasting triglycerides
 - weight.

Endpoints may include but are not necessarily limited to those listed earlier.

The impact of anti-drug antibody (ADA) and its titers on LY3493269 clearance and drug effect, if applicable, may be evaluated.

9.6 Safety and Tolerability Assessments

9.6.1 Adverse events

Where changes in severity are recorded in the Case Report Form (CRF), each separate severity of the AE will be reported in the listings, only the most severe will be used in the summary tables. A pre-existing condition is defined as an AE that starts before the participant has provided written informed consent and is ongoing at consent. A non-TEAE is defined as an AE which starts after informed consent but prior to dosing. A TEAE is defined as an AE which occurs postdose or which is present prior to dosing and becomes more severe postdose.

All AEs will be listed. TEAEs will be summarized by treatment, severity and relationship to the study drug. The frequency (the number of AEs, the number of participants experiencing an AE and the percentage of participants experiencing an AE) of TEAEs will be summarized by treatment, Medical Dictionary for Regulatory Activities (MedDRA) version 23.0 system organ class and preferred term. The summary and frequency AE tables will be presented for all causalities and those considered related to the study drug by the investigator. Any serious AEs (SAEs) will be listed.

Any AEs of special interest will be summarized and listed, these include cardiovascular events, gastrointestinal events (eg. , nausea, vomiting, diarrhea), hypersensitivity reactions, acute pancreatitis, and hypoglycemic events.

Discontinuations due to AEs will be listed.

9.6.2 Glucose Monitoring and Hypoglycemia

During the study, blood glucose concentrations will be monitored for safety assessments. Glucose data will be listed and summarized by treatment together with changes from baseline, where baseline is defined as Day 1 predose.

Hypoglycemic events will be appropriately recorded in the CRF. In the case of a hypoglycemic event, the actual blood glucose value, if measured, will be recorded in the CRF, together with

any treatments administered. Each category of hypoglycemic events (defined below) will be listed and summarized by treatment. Hypoglycemia is defined as follows:

- **Level 1 Hypoglycemia, Plasma glucose (PG) <70 mg/dL (3.9 mmol/L) and ≥ 54 mg/dL (3.0 mmol/L):**

Level 1 hypoglycemia can alert a person to take action such as treatment with fast-acting carbohydrates. Providers should continue to counsel participants to treat hypoglycemia at this glucose alert value.

- **Level 2 Hypoglycemia, PG <54 mg/dL (3.0 mmol/L):**

This is also referred to as documented or blood glucose confirmed hypoglycemia with glucose <54 mg/dL (3.0 mmol/L). This glucose threshold is clinically relevant regardless of the presence or absence of symptoms of hypoglycemia.

- **Level 3 Hypoglycemia: Severe hypoglycemia (in adults):**

A severe event characterized by altered mental and/or physical status requiring assistance for treatment of hypoglycemia. For example, participants had altered mental status, and could not assist in their own care, or were semiconscious or unconscious, or experienced coma with or without seizures, and the assistance of another person was needed to actively administer carbohydrate, glucagon, or other resuscitative actions. Glucose measurements may not be available during such an event, but neurological recovery attributable to the restoration of glucose concentration to normal is considered sufficient evidence that the event was induced by a low glucose concentration.

- **Nocturnal Hypoglycemia:**

Nocturnal hypoglycemia is a hypoglycemia event (including severe hypoglycemia) that occurs at night and presumably during sleep.

Investigator review of glucose results clinically indicative of hypoglycemia will be required.

To avoid duplicate reporting, all consecutive PG values <70 mg/dL (3.9 mmol/L) occurring within a 1-hour period may be considered to be a single hypoglycemic event

9.6.3 Concomitant medication

Concomitant medication will be coded using the World Health Organization (WHO) drug dictionary (Version WHODD MAR20B3). Concomitant medication will be listed.

9.6.4 Clinical laboratory parameters

All clinical chemistry and hematology data will be summarized by parameter and treatment together with changes from baseline, where baseline is defined as the Day 1 predose assessment. Clinical chemistry, hematology and urinalysis data will be listed. Additionally, clinical

chemistry, hematology and urinalysis data outside the reference ranges will be listed and flagged on individual participant data listings.

9.6.5 Vital signs

Vital signs data will be summarized by treatment together with changes from baseline, where baseline is defined as the Day 1 predose assessment. Figures of mean vital signs and mean changes from baseline profiles will be presented by treatment.

Values for individual participants will be listed.

Changes from baseline values will be analyzed using a repeated measurement mixed effect model. The model will include treatment, timepoint, and treatment-by-timepoint interaction as fixed effects; participant will be included as a random effect. Baseline will also be included as a covariate in the model. An unstructured covariance structure will be used to model the covariance between a participant's multiple observations, with an alternative structure to be used if the model fails to converge, using a measure such as Akaike's information criterion to decide which structure will be used. The difference in least-square treatment means, comparing LY3493269 (test) and placebo (reference), along with the 90% CI, will be reported. Example SAS code for the analysis:

```
proc mixed data=xxx;
  class time treat subject;
  model change = treat time treat*time base /residual ddfm=kr;
  repeated day / subject=subject type=un;
  lsmeans treat*day / cl pdiff alpha=0.1;
  ods output lsmeans=lsm diffss=estims;
run;
```

9.6.6 Electrocardiogram

The ECG data will be obtained directly from the 12-lead ECG traces. These data include the PR, QT, QRS duration, RR and HR. In addition, QTcF will be calculated as follows:

$$QTcF = \frac{QT}{\sqrt[3]{\frac{60}{HR}}}$$

The ECG data will be summarized by treatment together with changes from baseline, where baseline is defined as the mean of the triplicate Day 1 -0.5 h, -0.25, and predose assessments. Figures of mean ECG data and mean changes from baseline will be presented by treatment. The frequency of participants with a maximum increase from baseline in QTcF interval will be summarized for each treatment according to the following categories: >30 ms and >60 ms. In addition, the frequency of participants with QTcF postdose values, according to the following categories: >450 ms, >480 ms and >500 ms, will be summarized by treatment.

Plasma PK Concentration versus delta and double delta ECG parameter analysis

A plasma LY3493269 concentration-ECG parameter analysis will be performed to assess the relationship between changes from baseline (mean of Day 1 -0.5 h, -0.25 h, and predose

triplicate assessments) in ECG parameters (QTc, PR interval, QRS duration, and HR) and plasma LY3493269 concentrations across all treatments. The change from baseline adjustment will be based on individual participant's Day 1 -0.5 h, -0.25 h, and predose values. Further details on how these will be calculated:

- Calculate the baseline ECG value for each participant, which is the mean of ECG parameter values of each individual participant over 3 predose time points at Day 1.
- Calculate the change from baseline at each timepoint for each individual participant.
- Calculate the mean ECG parameter value across all participants at baseline.
- For each participant subtract the mean ECG parameter value from their own individual observed ECG parameter value. This will be each participant's centered ECG parameter value.
- BLQ LY3493269 concentration data will be imputed to the lower limit of quantification/square root(2) for the purposes of the analysis.

The relationship between LY3493269 concentrations and ECG parameters will be explored graphically by plotting delta ECG parameter values against LY3493269 concentrations, including all post dosing timepoints.

A mixed effects analysis model will be employed with change from baseline in ECG parameter as the dependent variable, LY3493269 concentration and centered ECG parameter value as continuous covariates, treatment and time as categorical factors, and a random intercept and slope per participant. Treatment will be fitted as a binary variable (Placebo, or LY3493269). The model will have the form:

$$\Delta ECG_{ijkl} = (\theta_0 + \eta_{0,i}) + \theta_1 TRT_j + (\theta_2 + \eta_{2,i}) C_{ijkl} + \theta_{3k} TIME_k + \theta_{4l} Day_l + \theta_5 TIME_k \times DAY_l + \theta_6 (ECG_{i,j,k=0,l=0} - \overline{ECG_{k=0,l=0}}) + \varepsilon_{ijkl}$$

where ΔECG_{ijkl} is the change from baseline in ECG parameter for participant i in treatment j at time k after dosing on day l . θ_0 is the population mean intercept in the absence of treatment effect, $\eta_{0,i}$ is the random effect associated with the intercept term θ_0 , θ_1 is the fixed effect categorical variable associated with treatment TRT_j , θ_2 is the population mean slope of the assumed linear association between concentration and ΔECG_{ijkl} , $\eta_{2,i}$ is the random effect associated with the slope θ_2 , C_{ijkl} is the concentration for participant i in treatment j , time k , and day l , θ_{3k} is the fixed effect associated with time after dose k on the same day, θ_{4l} is the fixed effect associated to day l , θ_5 is the fixed effect associated with the interaction between time and day, θ_6 is the fixed effect associated with baseline $ECG_{i,j,k=0,l=0}$, $\overline{ECG_{k=0,l=0}}$ is the overall mean of $ECG_{i,j,k=0,l=0}$ (the mean of all the baseline ECG parameter values, at day 0, time 0), and ε_{ijkl} is the residual error. It will be assumed the random effects are multivariate Gaussian distributed with mean vector $\mathbf{0}$ and an unstructured covariance matrix G , whereas the residuals, ε_{ijkl} , are Gaussian distributed with mean 0 and variance r .

If the model fails to converge, the interaction term will be omitted from the model, with day also omitted and time redefined to be time after the first dose if the model still fails to converge. The random effects may reduce to fixed effects and a different covariance structure may be used if there are further convergence issues.

The predicted mean change from baseline and placebo-corrected change from baseline in ECG parameter (Δ ECG and $\Delta\Delta$ ECG respectively) at the observed geometric mean C_{max} of each treatment (slope estimate * C_{max} + treatment effect) and two-sided 90% CI at different dose levels will be calculated. Residual plots will be produced to assess the adequacy of the model. The hysteresis loop plot between QTcF change from baseline concentration may be generated within 24 hours.

Example of SAS code as follows:

```
proc mixed data=xxxx;
by param;
class treat time subject;
model  $\Delta$ ECG = treat time baseline_ECG PKconc / solution cl alpha=0.1 ddfm=kr;
random intercept PKconc / type=un subject=subject;
estimate 'Placebo' intercept 1 treat 1 0 PKconc 0/ CL alpha=0.1;
estimate 'XX mg LY3493269' intercept 1 treat 0 1 PKconc [cmax XXmg] / CL
alpha=0.1;
estimate 'XX mg LY3493269 - Placebo' treat -1 1 PKconc [cmax XXmg] / CL
alpha=0.1;
ods output covparms=covp (where= (covparm=" Residual"));
ods output solutionF=sol;
ods output estimates=estim;
run;
```

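### The last convergence step for the concentration-ECG model lets both participant random effects go with no within-participant covariance required in their place; if used that way, the 90% CIs are too narrow

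*SAP*

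**What the plan says.** SAP Section 9.6.6 specifies a mixed model for change from baseline in QTc, PR, QRS and heart rate. Concentration and centred baseline are covariates, with "treatment and time as categorical factors, and a random intercept and slope per participant". Treatment is binary, placebo or LY3493269. The covariance matrix of the random effects is unstructured, and the residuals have mean zero and one variance r; no residual correlation within a participant is stated. The example code has "random intercept PKconc / type=un subject=subject".

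The output is described as "The predicted mean change from baseline and placebo-corrected change from baseline in ECG parameter", evaluated at the observed geometric mean Cmax of each treatment with a two-sided 90% CI. The code obtains the placebo-corrected value from "estimate 'XX mg LY3493269 - Placebo' treat -1 1 PKconc [cmax XXmg] / CL", that is, the treatment coefficient plus the slope times Cmax.

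Non-convergence is handled in three steps. The time-by-day interaction is dropped. If that fails, day is dropped and time is redefined as time after the first dose. If problems remain: "The random effects may reduce to fixed effects and a different covariance structure may be used if there are further convergence issues".

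**The concern.** The model has only two sources of within-participant correlation, the random intercept and the random slope. The last fallback names the random effects in the plural, does not say which goes first, does not require either to stay, and names no replacement structure. The output still depends on the treatment coefficient, which is estimated between participants. If both random terms go and the residuals stay as specified, the standard error of that coefficient is computed as though every record came from a different person.

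At stake is the width of the 90% CI around the placebo-corrected QTcF change, and likewise for PR, QRS and heart rate. An interval that is too narrow makes an upper QTcF bound look more reassuring than the data justify. Convergence trouble is plausible with an unstructured two-by-two matrix in about 40 participants, and the SAP itself provides for it in three stages.

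**Working it through.** The SAP gives no figure for this analysis, so there is none to reproduce.

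**Inputs from the documents**
- Participants: 8 active and 2 placebo completers in each of 4 cohorts (Protocol 9.2), so 32 active and 8 placebo.
- Matched post-dose ECG/PK times (Protocol 1.3): Day 1 at 1, 4, 6, 12 h (4); Day 3 predose and 1, 4, 6, 12 h (5); Days 4, 5, 6, 8, 15 (5). Total m = 4 + 5 + 5 = 14. Day 2 has ECGs but no PK.
- Placebo samples are not to be assayed (Protocol 8.5.1); their concentration is taken as 0.
- Concentration scale: predicted average 56.6 ng/mL at 8 mg and 341 ng/mL at 48 mg (Protocol Table 4.1).

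**Assumed, because the documents are silent**
- Residual SD 6 ms; participant intercept SD 0 to 8 ms; slope SD 0 to 2 ms per 100 ng/mL.
- Half-life 48 to 168 h; between-participant CV of concentration 50 to 100%.

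**Reading 1: both random terms dropped, residuals independent.** With ICC = SD²/(SD² + 6²), the usual design effect gives

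reported SE / true SE = 1/√(1 + (m − 1) × ICC), and coverage = 2Φ(1.645 × ratio) − 1.

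For example, at SD 3 ms: ICC = 9/45 = 0.20; ratio = 1/√(1 + 13 × 0.20) = 1/√3.6 = 0.53; coverage = 2Φ(0.867) − 1 = 61%. The direct calculation compares the model-based SE of the full contrast (treatment plus slope times Cmax) with its true SE on the planned design. Ratios are rounded after the coverage is computed.

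| Intercept SD (ms) | ICC | Design-effect ratio | Coverage | Direct ratio | Coverage |
|---|---|---|---|---|---|
| 0 | 0 | 1.00 | 90% | no narrowing | 90% |
| 2 | 0.10 | 0.66 | 72% | 0.68 | 73% |
| 3 | 0.20 | 0.53 | 61% | 0.54 | 63% |
| 4 | 0.31 | 0.45 | 54% | 0.46 | 55% |
| 6 | 0.50 | 0.37 | 45% | 0.38 | 46% |

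If slopes also vary between participants, the direct calculation gives 32 to 55%. A simulation (150 data sets per setting, so a Monte Carlo error of up to about 4 percentage points) agrees:

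| Intercept SD; slope SD | No random effects | Random intercept only | Intercept and slope |
|---|---|---|---|
| 2; 0 | 69% | 91% | 94% |
| 4; 0 | 51% | 87% | 88% |
| 4; 1 | 42% | 80% | 87% |
| 6; 1 | 36% | 85% | 88% |

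At SD 4 with no slope variation, the mean CI width was 2.96 ms without random effects and 6.07 ms with a random intercept.

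**Reading 2: participant fitted as a fixed effect.** Columns: intercept, treatment, concentration, 13 time indicators and centred baseline make 17; adding 40 participant indicators gives 57. The rank is 40 + 13 + 1 = 54. The intercept, treatment and baseline columns are linear combinations of the participant indicators, because each is constant within a participant. The treatment coefficient and the placebo-corrected change are therefore non-estimable; only the common slope survives. Adding 40 participant slopes gives 97 columns of rank 40 + 13 + 32 = 85 (placebo slopes are empty at zero concentration), and the common slope is lost too.

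**Keeping at least a participant random intercept.** The contrast stays estimable. Calculated coverage is 90% if slopes do not vary, and 74 to 87% if they do.

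**The case against.** A reader might infer that the fallback must end in either a non-estimable contrast or a badly narrow interval. The text does not support that. The same sentence permits a different covariance structure, and once both random terms are gone the only covariance left to change is that of the residuals. Compound symmetry there is equivalent to a random intercept. Reducing only the slope is also open. This stands: a sound route lies within the wording. But it is optional. By contrast, the SAP's models for vital signs (9.6.5) and PD (9.4.2) move to an alternative covariance structure and do not mention converting random effects to fixed.

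The participant-as-fixed reading is strained. The SAP writes each term as a population value plus a participant deviation, so reducing to fixed effects most naturally means that the deviations disappear. Were participants fitted as fixed, the estimate statements would return no interval, which could not pass unnoticed. This also stands.

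The size depends on an ICC that the documents do not give, and low values cannot be excluded. In a rough simulation (100 runs per setting, not in PROC MIXED, no slope variation), the full model failed to converge in 66%, 62% and 32% of runs at intercept SD 0, 1 and 3 ms. Coverage without random effects was 93%, 83% and 63%. Trouble was thus commonest where dropping the terms costs least. That tempers the worst figures but does not remove the problem at 3 ms. An ICC of exactly zero is also unlikely, since one baseline mean is subtracted from all of a participant's records and its error is shared among them.

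Finally, it is tempting to call this interval the study's QT conclusion. QT is not among the objectives or endpoints, no threshold or decision rule is attached to the CI, and SAP 9.6.6 also gives ECG summaries and categorical QTcF counts that do not use this model.

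**Conclusion.** The concern holds as a flaw in a permitted rule. If the last step is taken by dropping both random terms with the residuals left as specified, a nominal 90% CI for the placebo-corrected change covers roughly 73% at ICC 0.1, 61 to 63% at 0.2 and 45 to 46% at 0.5; at ICC 0 nothing is lost. These figures rest on 14 matched records per participant, 32 active and 8 placebo participants, and an assumed ICC with no slope variation; slope variation makes them worse. The non-estimable outcome follows from algebra alone, but it belongs to the less natural reading and would be seen.

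The harm is conditional on reaching a permissive third step, and it is confined to a supportive safety analysis that Protocol 9.4.2 commits to for QTcF. The primary TEAE endpoint is untouched. A reader might also suppose that dropping only the slope restores full validity; it does so only if slopes are alike across participants.

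**What to change.** Replace the last fallback sentence in SAP Section 9.6.6 with:

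> If further convergence problems occur, first set the intercept-slope covariance to zero, then drop the random slope. A participant random intercept, or an equivalent within-participant residual covariance such as compound symmetry, is always retained, and participant is not fitted as a fixed effect. If the random slope is dropped, this is reported, because the 90% CI may be somewhat narrow if slopes differ between participants.

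The cost is a short text replacement in the SAP. No new data are needed, and the model to be fitted first does not change.

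### SAP 9.6.6: the example code for the concentration-ECG model leaves out the DAY and TIME × DAY terms of the stated model, and the centering step names the observed rather than the baseline ECG value

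*SAP*

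**What the plan says.** All of this is in SAP 9.6.6.

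- **Equation.** The fixed part has treatment (placebo or LY3493269), concentration, hour after dose on the same day, day, and a term that "is the fixed effect associated with the interaction between time and day". The remaining covariate is the participant's baseline ECG value minus the overall baseline mean. Each participant has a random intercept and slope. If the model does not converge, the interaction is dropped. Only if it fails again is day dropped, and time is then redefined to run from the first dose.
- **Code.** It is labelled an example, but it is the only code given for this model. Its class statement is "class treat time subject" and its fixed effects are "treat time baseline_ECG PKconc / solution cl alpha=0.1 ddfm=kr". It has no day variable and does not define time.
- **Centering step.** "For each participant subtract the mean ECG parameter value from their own individual observed ECG parameter value". The mean in question is taken across participants at baseline. The text that follows names the resulting centered value as the model covariate.
- **Predictions.** Change from baseline (ΔECG) and placebo-corrected change (ΔΔECG) are predicted at the geometric mean Cmax, "and two-sided 90% CI at different dose levels will be calculated", using "slope estimate * C_{max} + treatment effect". The two single-arm statements are "estimate 'Placebo' intercept 1 treat 1 0 PKconc 0/ CL alpha=0.1" and "estimate 'XX mg LY3493269' intercept 1 treat 0 1 PKconc [cmax XXmg] / CL". Neither lists a coefficient for time or baseline.

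**The concern.** A programmer who follows the code and one who follows the equation can fit different models, and the SAP does not say which prevails. Two consequences matter.

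First, without a day term, a shift between Day 1 and later days that affects both arms has no place of its own in the model. Concentration also rises from Day 1 to Day 3 in the active arm, so part of the shift can be read as a concentration effect.

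Second, a covariate built from the post-dose ECG value adjusts the outcome for itself and can hide a real effect.

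The analysis covers QTc, PR, QRS and heart rate. Protocol 9.4.2 commits to the QTcF part, and Protocol 2.2.1 reports a dose-dependent heart-rate increase in the first-in-human study. This is a place where a small spurious effect or a masked real one would mislead.

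**Working it through.** The SAP gives no figure to reproduce here. The check compares the two specifications and sizes the consequences.

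**1. Design points.** SAP section 5 gives 4 cohorts of 8 active and 2 placebo: 4 × 8 = 32 active, 4 × 2 = 8 placebo. Protocol 1.3 gives the post-dose triplicate ECGs that have a matching LY3493269 sample: Day 1 at 1, 4, 6, 12 h; Day 3 at predose, 1, 4, 6, 12 h; and one each on Days 4, 5, 6, 8 and 15. That is 4 + 5 + 5 = 14 day-by-time cells. Day 2 has ECGs but no PK samples.

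**2. Does the code span the stated model?** Columns are intercept 1, treatment 2, time levels, baseline 1, concentration 1. Treatment and time each bring one redundancy.

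| Fixed effects | Time levels | Columns | Rank |
|---|---|---|---|
| Code, time after most recent dose | 10 | 1+2+10+1+1 = 15 | 13 |
| Code, time after first dose | 14 | 1+2+14+1+1 = 19 | 17 |
| Stated model with TIME, DAY, TIME × DAY | 14 cells | – | 17 |

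The stated model joined to the time-after-first-dose version also has rank 17, so those two are the same fixed-effects model. Under the equation's own definition of time, the code loses 17 − 13 = 4 dimensions: the hours 1, 4, 6 and 12, each shared by Day 1 and Day 3. If the later visits were coded as hour 0 of their own day, only 5 time levels would remain, the rank would fall to 8, and the loss would be 9.

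**3. Size of the drift effect.** The predicted quantity is ΔΔECG = treatment effect + slope × Cmax. Four sets of simulations had no drug effect and a drift after Day 1 common to both arms. The half-life is redacted in the protocol, so it is assumed.

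| Assumptions | 3 ms drift | 5 ms drift | Comparator |
|---|---|---|---|
| Half-life 5 days, exposure log-SD 0.8, residual SD 6 ms | +1.0 ms | +1.8 ms | stated model: about 0 |
| Half-life 5 days, residual SD 6 ms | +1.3 ms | +2.1 ms | stated model: about 0 (−0.3) |
| Half-life 24 to 168 h | +0.7 to +1.0 ms | +1.1 to +1.5 ms | stated model: about 0 |
| Visits after Day 3 given their own time-after-dose levels | +0.2 ms | +0.3 ms | time after first dose: +0.1 and 0.0 |

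As a share of the drift, this runs from 0.2/3 = 7% to 1.3/3 = 43%, and from 0.3/5 = 6% to 2.1/5 = 42%.

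**4. Size of the centering effect.** For participant i at time t, ΔECG(i,t) = ECG(i,t) − base(i). If the covariate is ECG(i,t) − mean baseline, then ΔECG(i,t) = covariate − [base(i) − mean baseline]. The bracket is constant within a participant, so a covariate coefficient of 1 plus a participant intercept reproduces the outcome exactly and leaves nothing for concentration.

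With a true 10 ms effect, the baseline covariate recovered 10.0 ms. The time-matched observed covariate with a participant random intercept gave:

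- 4.0 ms in one set (sampling SD 3.8 ms, against 2.0 ms with the baseline covariate);
- 3.0 ms in another (0.9 to 7.7 ms as the assumed intercept variance changed);
- about 3 ms in a third;
- −0.8 to 0.0 ms when fitted by REML to the degenerate solution (covariate coefficient 1.000, residual variance about 1e-10).

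The loss is small in two other cases. One post-dose value per participant gave 9.3 ms. Least squares with no participant intercept gave a slope of 0.094 against a true 0.100.

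**5. The ESTIMATE statements.** The ΔΔECG contrast is estimable under both time codings and matches the SAP's formula. The two ΔECG vectors are not estimable if unlisted time coefficients are zero. They are estimable if the intercept is spread equally (1/10 or 1/14 per level). In that case Days 4 to 15 carry 5/10 = 50% or 5/14 = 36% of the time weight in a prediction made at Cmax, so the weighting deserves to be stated.

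**The case against.** The strongest reply is that the code is only an example and the equation governs. The code does not define time; if it means time after first dose, the fit equals the stated model and the drift effect vanishes. The equation, its description of the last coefficient and the variable name `baseline_ECG` all point to baseline, so *observed* probably means the observed baseline value. A literal time-matched fit could be degenerate and quickly noticed. The drift figures rest on an invented drift and an assumed half-life, and even +1.0 ms is half of the 2.0 ms sampling SD above. The primary endpoint is TEAEs, the study is not powered for hypothesis tests, and ECGs also receive descriptive summaries and QTcF outlier categories.

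Most of this stands as a limit on size and on intent. It does not remove the inconsistency. The equation defines time as hour after dose on the same day, and the text allows day to be dropped only after two failures to converge, with time then redefined. The code applies the reduction with no such note. A bias smaller than the sampling SD is still avoidable.

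Two stronger readings are tempting. A reader might infer that the ΔECG predictions cannot be estimated at all. That requires unlisted time coefficients to be taken as zero, and the documents do not say how the software treats them. A reader might also infer that ΔECG is predicted at a baseline of 0 ms. With an assumed 400 ms mean and a baseline coefficient of −0.1 to −0.5, a raw covariate would shift ΔECG by 0.1 × 400 = 40 to 0.5 × 400 = 200 ms. But the text says the covariate is centered, in which case a coefficient of 0 is right, and ΔΔECG is unaffected either way.

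**Conclusion.** SAP 9.6.6 is internally inconsistent on the concentration-ECG model in two places, and both should be corrected.

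(a) The code omits DAY and TIME × DAY. With time as the equation defines it, an assumed 3 ms common drift produces roughly +0.2 to +1.3 ms of spurious placebo-corrected QTcF. It produces essentially none if time is coded from first dose. The size depends on the drift, half-life, variance and time coding assumed; the influence of the planned random concentration slope is not quantified here.

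(b) The centering step says *observed* where the equation uses baseline. Taken literally as a time-matched value, it would remove most of a real effect under the main settings tried. The documents do not show that this is intended, and the equation suggests it is not.

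The placebo-corrected contrast is sound as written. For the single-arm predictions the point is only that the time weights, the treatment level order and the centered status of `baseline_ECG` are left implicit.

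**What to change.** In SAP 9.6.6:

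1. In the centering step, replace *observed* with *baseline*, so that each participant's baseline ECG value is centered on the overall baseline mean.
2. In the code, use `class treat day time subject;` and `model dECG = treat time day time*day cbase_ECG PKconc`, where `cbase_ECG` is the centered baseline, keeping the existing options and random statement. Alternatively, keep the single time factor and state that it is nominal time after first dose.
3. In the two change-from-baseline ESTIMATE statements, write out the TIME, DAY and TIME × DAY weights. State the order of the treatment levels, because the coefficients assume that placebo sorts first.
4. Leave the placebo-corrected statement as it is, apart from confirming that level order.

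The cost is SAP text and code only. No data collection, sample size or visit changes.
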